This study is a cross-sectional CRXO in that, each cluster-period consists of different individuals (patients). The order in which the interventions are delivered to each cluster (ward) is randomized to control for potential period effects. Within Foothills Hospital there are 40 wards which will be observed over a 12-month period. Each ward is randomly assigned to administer one of the two interventions for the first 6-month period (Period 1). In the second 6-month period (Period 2), the ward will administer the other intervention. Within each ward (cluster) there are two cluster-periods. Study outcomes during Period 1 and Period 2 intervention will be compared in both arms (NPT and centralized laboratory testing).

NPT testing can deliver results within several hours, while typically off-site testing takes one to two days. If NPT and the off-site testing deliver identical test results as our pilot data suggest, we can follow the clinical outcomes for each arm without the confounder of differences in test performance. As a contingency, if variation in test performance characteristics is found, analysis of patient outcomes will take this into consideration.

For patients without CDI, the antibiotics, and in many cases, the isolation, are unnecessary. NPT testing has the potential to avoid this unnecessary use of antibiotics and to avoid costly isolation procedures for the day+ that standard testing requires. It also enables a better-directed diagnostic process for the cause of diarrhea. For patients who are positive for CDI, the earlier test result will influence downstream events such as initiation of antibiotic therapy, resolution of disease, hospitalization days, and other clinical outcomes.

We hypothesize that NPT for CDI will result in reduced patient isolation days in the hospital, decreased morbidity and mortality, reduced unnecessary antibiotic use and overall reduced costs to the health care system, including both hospital and laboratory.

Previous data has indicated that the mean number of patients a ward is 39/month ($SD=43$) for a total of 1578 patients in a 6-month period and the mean number of negative patients is 33/month ($SD=34$) for a total of 1300 negative pts in a 6-month period. The inclusion criteria will be diarrhea in adult patients admitted to four acute care hospitals in the Calgary region being tested for CDI. Outpatients and patients in the emergency room will be excluded.

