Our primary endpoint is to examine the differential effect of NPT on the duration of contact precautions (i.e. patient isolation days). Secondary outcomes will compare turn-around times from specimen submission to result, days of hospitalization, the number of days of antibiotic therapy, the incidence of CDI, severe CDI, and in-hospital mortality. A comprehensive economic evaluation will be performed to determine the cost of testing, patient isolation, and hospitalization for all patients in the control and treatment arms.

Methods:

Contact precautions (i.e. patient isolation) due to CDI will be defined as an order by healthcare workers for contact precautions within the 7-day infection window of a CDI diagnosis. The length of time on contact precautions will be defined as the calendar date contact precautions are completed or patient discharge date minus the calendar date contact precautions are ordered. Data on contact precautions will be extracted from the clinical patient management system in Calgary, known as Sunrise Clinical Manager (SCM). It is used extensively in all Calgary acute care facilities and emergency departments. These data include patient identifiers (e.g. patient health number, names, date of birth), start and stop dates of isolation, facility, and patient care unit where isolation order was placed, and reason for isolation (e.g. CDI, diarrhea). These data will be linked to the specimen results tested for CDI by the patient's Personal Health Number (PHN). Turn-around times from specimen submission to result will be provided by Calgary Laboratory Services. Days of hospitalization will be defined as the difference between the admission and discharge date. The specimen results will be linked to the Discharge Abstract Database using the patient's PHN to determine during which acute care encounter the specimen was collected and the admission/discharge dates of that encounter. Antibiotic therapy will be defined as the administration of antibiotics initiated on the day of and up to 48 hours after specimen collection for CDI testing. Total days of antibiotic therapy during the acute care encounter will be defined as the calendar date antibiotic therapy is completed minus the calendar date antibiotic therapy is ordered. The data will be extracted from SCM.

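### The primary endpoint has a value only where contact precautions were ordered, and the plan does not say how a tested patient with no order is scored

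*Combined protocol and SAP*

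**What the plan says.** Study Objectives names the duration of contact precautions, in patient isolation days, as the primary endpoint. Methods defines contact precautions due to CDI as "an order by healthcare workers for contact precautions within the 7-day infection window of a CDI diagnosis", and their length as "the calendar date contact precautions are completed or patient discharge date minus the calendar date contact precautions are ordered". The data are isolation order records with start date, stop date and reason, linked to specimen results by health number.

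The population is wider than patients with an order. In Study Objectives the inclusion criteria are "diarrhea in adult patients admitted to four acute care hospitals in the Calgary region being tested for CDI"; an isolation order is not among them. The economic evaluation in the same section covers all patients in both arms. The rationale there is that NPT has the potential "to avoid costly isolation procedures for the day+ that standard testing requires".

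Two other places bear on the point. Background and Significance says that isolation for acute unexplained diarrhea starts pre-emptively as routine, and that its duration depends largely on the test result. The example model in Data Analysis takes the hours a patient spends in isolation as a possible outcome. Neither place gives a rule for a patient who was never isolated.

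**The concern.** A stop date minus an order date needs an order date. A tested patient without one has no primary-endpoint value unless the plan supplies it, and it does not. If the formula is applied as written, the analysis compares patients with an order under NPT with patients with an order under central testing.

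Having an order is an event after randomisation. Study Objectives expects NPT results within several hours and off-site results in one to two days, so the assigned test could influence whether an order is placed. A patient whose order is pre-empted by a fast negative would leave the NPT comparison, while the counterpart under central testing would stay in with a short isolation. Randomising wards does not protect a comparison selected in this way. The days saved by preventing isolation would also not be counted, although they are part of the question the trial asks.

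Patients who are never isolated can occur in both arms. What matters is a difference between arms in their share.

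**Working it through.** There is no figure in the plan to reproduce: it gives no share of patients isolated, no mean or SD of isolation days, and no target effect. The two illustrations below show direction and sensitivity only. Differences are NPT minus central, in days.

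**Illustration 1.** All inputs are assumed: 90% of tested patients isolated under central testing; a share a of tested patients has isolation prevented by NPT and would have had 1.5 days; the other isolated patients have 4 days under central testing and 3.5 under NPT.

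- Order-only difference = 3.5 − [(0.90 − a) × 4 + 1.5a] / 0.90
- Per-tested difference = (0.90 − a) × 3.5 − [(0.90 − a) × 4 + 1.5a]

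| a | Order-only | Per tested patient |
|---|---|---|
| 0 | 3.5 − 3.60/0.90 = −0.50 | 3.150 − 3.600 = −0.45 |
| 0.05 | 3.5 − 3.475/0.90 = −0.36 | 2.975 − 3.475 = −0.50 |
| 0.10 | 3.5 − 3.35/0.90 = −0.22 | 2.80 − 3.35 = −0.55 |
| 0.20 | 3.5 − 3.10/0.90 = +0.06 | 2.45 − 3.10 = −0.65 |

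As more isolations are prevented, the true saving grows and the order-only estimate shrinks. The order-only difference is zero when 3.5 × 0.90 = 3.60 − 2.5a, so a = 0.18, which is 0.18/0.90 = 20% of isolations.

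**Illustration 2.** The share negative comes from the 6-month totals in Study Objectives: 1300/1578 = 82.4%. The rest is assumed: everyone isolated under central testing, negatives for 2 days and positives for 10; NPT shortens each remaining negative isolation by 0.5 day and prevents a fraction q of negative isolations.

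- Central mean = 0.824 × 2 + 0.176 × 10 = 3.41
- NPT per-tested mean = 0.824(1 − q) × 1.5 + 1.76
- NPT order-only mean = that value / [0.824(1 − q) + 0.176]

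| q | Order-only | Per tested patient |
|---|---|---|
| 0 | −0.41 | −0.41 |
| 10% | 3.13 − 3.41 = −0.28 | 2.87 − 3.41 = −0.54 |
| 30% | 3.49 − 3.41 = +0.08 | 2.63 − 3.41 = −0.78 |

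Here the order-only sign changes at q of about 26%: 1.5x + 1.762 = 3.409(x + 0.176) gives x = 0.608, and 1 − 0.608/0.824 = 0.26. That is 0.824 × 0.26, or about 22% of all isolations.

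Varying negative isolation from 1.5 to 3 days and shortening from 0 to 1 day, at q = 30% the per-tested difference runs from −0.37 to −1.32 and the order-only difference from +0.49 to −0.36. If NPT shortens nothing and only prevents, the order-only sign is wrong even at q = 10% (+0.13 against −0.16, with negatives at 2 days).

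**Dependency on the diagnosis wording.** Read literally, the Methods definition ties the order to a CDI diagnosis. Only 1578 − 1300 = 278 patients per 6 months (17.6%) could then have a value, or about 174 at the 11% positive implied by the 89% negative after PCR in Background and Significance. A zero rule added on top of that wording would score the remaining 82% to 89% as 0 in both arms.

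**The case against.** The strongest reply is that the plan nowhere excludes these patients. The Methods formula says how to measure time on precautions; it does not define who is analysed. The population is everyone tested, and the only model shown is at patient level, where hours in isolation for someone never isolated are naturally zero. This stands in part: exclusion is what follows from the formula, not a stated rule. But the model is offered as an example, uses hours where Methods uses calendar dates, and gives no scoring rule. On a primary endpoint, silence leaves the choice open until data are in hand.

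The second reply is that isolation is triggered by diarrhea, before any result. A fast negative would then mainly shorten an isolation already ordered. That patient has an order date and stays in, with 0 days if the order starts and stops on one date. The rationale about avoiding the waiting day fits shortening as well as prevention. This largely stands, and it is why few orders are likely to be prevented. It does not close the gap: the plan calls pre-emptive CDI management common, not universal.

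The third reply is that the distortion depends on prevented stays being shorter than the rest. In illustration 1, if they were also 4 days, the order-only difference would be −0.50 at every a. That is correct, but the prevented days still go uncounted: at a = 0.10 the per-tested difference would be 0.80 × 3.5 − 0.90 × 4 = −0.80.

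**Conclusion.** The plan leaves the primary endpoint undefined for tested patients with no precautions order. Applied literally, the formula conditions the comparison on a post-randomisation event that the assigned test can influence, and it does not match the tested population or the all-patient economic evaluation. If NPT prevents some short isolations, the estimated benefit would shrink. The documents do not allow the size to be determined; given routine pre-emptive isolation it is probably small. If ordering is equal across arms and nothing is prevented, the problem has no practical effect on the conclusion.

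A reader might infer more: that the plan drops never-isolated patients, so the endpoint is biased against NPT and may show the wrong sign. The documents do not support this. No section states such an exclusion, and the Data Analysis model can be read as allowing zeros. A reversed sign needs extreme assumed inputs: either NPT prevents more than about a fifth of all isolations and the prevented stays are much shorter than the rest, or it prevents isolations without shortening any others. The first sits poorly with pre-emptive isolation, and the second with the plan's statement that duration depends largely on the result.

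**What to change.** Define the primary endpoint as isolation days per tested patient in each cluster-period. Count any contact-precautions order for diarrhea or for suspected or confirmed CDI, regardless of test result, that is in force at index specimen collection or placed after it. Assign 0 days only to tested patients with no such order. A patient already isolated at collection therefore contributes days, not a zero. Report by arm, as supportive results, the proportion ever isolated and the duration among those isolated.

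In the same edit, remove the restriction to a CDI diagnosis from the Methods definition; otherwise test-negative patients would be scored 0 whether or not they were isolated. The 7-day window then needs a stated anchor other than the diagnosis, such as the index specimen.

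No new data are needed: the order records carry a reason for isolation and are already to be linked to specimen results. The cost is a short rewrite of the endpoint definition. The small downside is more zeros in the outcome distribution, which the analysis must accommodate.

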A key issue in many settings, including ours, is that testing falls into a separate budget from the treatment of patients with CDI infections. This has the potential to distort the decision of whether to run a test and, if so, what sort of test. The distortions are of two types. First, the hospital may decide to order more tests than is optimal, since the tests are perceived as "free" from the perspective of decision-makers. At the same time, the diagnostic facility may choose low-cost, slow diagnostics, because the costs associated with delays in test results are borne by the hospital. This is a classic case of silos in health care costs inefficiently distorting policy decisions, with potentially negative results for both patient health and costs.

Many institutions follow the clinical practice guidelines provided by the Infectious Diseases Society of America for the management of *C. difficile* (Cohen et al., 2010). As part of routine Infection Prevention and Control (IPC) management, patients with acute diarrhea of unknown cause are pre-emptively placed in private rooms with additional contact precautions, which mandate the use of gowns and gloves for healthcare workers. This is also known as patient isolation. Investigation for gastrointestinal pathogens is typically initiated and the duration of patient isolation depends largely on the result of microbiological testing. When severe or complicated CDI is suspected, patients are initiated on empiric treatment as soon as the diagnosis is suspected. Generally, oral metronidazole is used for mild-to-moderate CDI and oral vancomycin for severe CDI. Among hospitalized patients with acute diarrhea, initiation of pre-emptive management for CDI is common. With requested CDI screening, 85% are negative on GDG screen and 89% are negative post PCR confirmation.

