We will also account for the severity of CDI. The epidemiological definition for severe CDI is that primarily proposed by Cohen *et al*. This definition has been used by infectious disease specialists in Alberta to guide the management and treatment of patients with CDI. Patients with severe CDI will have leukocytosis with a white blood cell (WBC) count $>15,000$ cells/ μ L OR an elevated serum creatinine (i.e. 200 μ mol/L or greater). The inpatient laboratory results that will be considered to meet the definition for severe CDI will be those collected within a 7-day infection window around the date the laboratory tested positive for *C. difficile*. The presence of either measure meeting the criteria within the defined infection window will qualify as meeting the definition of severe CDI. If either criterion is measured more than once during the infection window, the highest value will be used to represent the severity of CDI. The laboratory values will be provided by Calgary Laboratory Services and linked to the positive *C. difficile* test results. In-hospital, all-cause mortality will be defined as death occurring during the acute care encounter where specimens were collected for *C. difficile* testing.

We predict that, given the large number of patients and randomized study design, matching of patients by age, gender, and co-morbidities is not required. Potential hurdles in the study model are logistical challenges associated with building a testing and reporting system for a hospital on a 24hrs/7 days per week basis. The strength of the proposal lies in the scale and nature of the study which seeks to establish the medical and economic benefit of NPT versus centralized testing. The results could dramatically influence public health policy in this country and seek to bridge traditional silos, namely the laboratory and hospital budgets. Data on costs will be furnished by our partners at Calgary Laboratory Services and Alberta Health Services (Infection Prevention and Control).

Data Analysis:

In order to make the data generalizable to other settings, an appropriate econometric methodology to assess the impact of the impact of the NPT testing through multivariate regression is required. For example, consider the following potential model:

$$y_i = \beta_0 + \beta_1 POCT_i + \beta_2 Z_i + \beta_3 H_i + \beta_4 T_i + u_i$$

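### The primary endpoint is labelled as isolation due to CDI but selects orders by timing alone, so isolation ordered for another reason counts in full

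*Combined protocol and SAP*

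**What the plan says.** Study Objectives in the combined protocol and SAP names the primary endpoint as "the differential effect of NPT on the duration of contact precautions (i.e. patient isolation days"). Methods then gives the working definition. Contact precautions attributed to CDI are "defined as an order by healthcare workers for contact precautions within the 7-day infection window of a CDI diagnosis". Their length is "the calendar date contact precautions are completed or patient discharge date minus the calendar date contact precautions are ordered". The fields taken from the clinical patient management system (SCM) include start and stop dates, facility, care unit "and reason for isolation (e.g. CDI, diarrhea"). No sentence uses the reason to include, exclude or classify an episode.

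Background and Significance says that "patients with acute diarrhea of unknown cause are pre-emptively placed in private rooms with additional contact precautions", and that investigation for gastrointestinal pathogens is then usually begun. It also says that 89% of CDI requests are negative after PCR confirmation. Study Objectives gives the interval that the intervention changes: "NPT testing can deliver results within several hours, while typically off-site testing takes one to two days".

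**The concern.** The label and the rule differ. The label restricts the endpoint to isolation caused by CDI or its suspicion. The rule admits any contact-precautions order that falls in the window. An order for a resistant organism in the same week therefore qualifies and contributes its whole length, yet near-patient testing cannot shorten it.

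Such episodes carry no treatment effect and may be long. They pull the mean difference towards zero and widen the spread of an endpoint whose expected gain is about one day.

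The unused field also leaves the primary endpoint open. One analyst could filter on reason because of the label, another could apply the written rule, and both could say they followed the protocol. No blinding is described, so the choice should be fixed in advance.

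**Working it through.** **1. Text against text.** Selection of the episode: order date relative to a CDI diagnosis. Reason: extracted, not used. Clock: from the order date. No other section removes orders placed for another cause. The window's direction is not stated for this endpoint. For severe CDI it is "within a 7-day infection window around the date the laboratory tested positive for" the organism. In either direction, a window of a CDI diagnosis has no anchor date for a patient who tests negative.

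**2. Figure to reproduce.** None. The documents give no SD of isolation days, target difference, intracluster correlation, alpha or power. Everything below is illustration.

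**3. Mixture of episodes.** Assumed inputs: diarrhea/CDI isolation has mean 2.5 and SD 2.5 days, and near-patient testing saves 1 day; other-reason isolation has mean 10 and SD 10 days with no effect. Let f be the share of counted orders placed for other reasons. The same SD is used in both arms.

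- Effect = 1 × (1 − f)
- Mean = (1 − f) × 2.5 + f × 10
- Variance = (1 − f) × (2.5² + 2.5²) + f × (10² + 10²) − mean²
- Information ratio = [(effect / SD) / (1 / 2.5)]²

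f = 0.05: mean 2.375 + 0.5 = 2.875; variance 11.875 + 10 − 8.266 = 13.609; SD 3.69; effect 0.95; standardised effect 0.258 against 0.40; ratio 0.41.

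f = 0.10: mean 2.25 + 1 = 3.25; variance 11.25 + 20 − 10.563 = 20.688; SD 4.55; effect 0.90; standardised effect 0.198; ratio 0.24.

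These ratios are per counted order. If the filter drops the other-reason patients, the ratios per tested patient are 0.41/0.95 = 0.44 and 0.24/0.90 = 0.27.

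**4. What that does to power.** Every ward spends one six-month period in each arm, and Study Objectives gives 1578 patients per six months, so take 1578 per arm, two-sided 0.05. At f = 0.10 the standard error is 4.55 × √(2/1578) = 0.162 and 0.90/0.162 = 5.56, so power is above 99.9%; it is higher still at f = 0.05. Dividing 5.56 by the square root of an assumed design effect gives power at f = 0.10 of about 98% (design effect 2), 89% (3) and 70% (5).

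**5. Dilution alone, SD held fixed.** Same sample size and alpha, clustering ignored, true effect 1 day:

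| f | Power, SD 10 | Power, SD 5 | Required N multiplied by 1/(1 − f)² |
|---|---|---|---|
| 0 | 0.802 | 1.000 | 1.00 |
| 0.10 | 0.715 | 0.999 | 1.23 |
| 0.20 | 0.613 | 0.994 | 1.56 |
| 0.30 | 0.503 | 0.976 | 2.04 |

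**6. Days before the specimen.** If independent of later days, they add variance and leave the expected difference unchanged when balanced between arms. An assumed pre-specimen SD of 1 to 3 days multiplies the variance by 1.04 to 1.36 when the post-specimen SD is 5, and by 1.11 to 2.0 when it is 3. The documents give no delay from order to specimen.

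**The case against.** The strongest reply is that the intent is visible. The label names CDI and the example reasons are CDI and diarrhea, so a filter was probably meant. A reader might infer that the sponsor chose to count isolation for resistant organisms; the documents do not show that. They show a rule that, as written, does so.

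Second, the illustration does not match the population that the literal rule selects. A 1-day saving fits patients who test negative, because positive or discrepant near-patient results still go to the central laboratory for NAAT. Yet a window of a CDI diagnosis gives those negative patients no anchor. This stands, and is why the window must be repaired along with the reason.

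Third, a filter on reason has a risk of its own. Ward staff record the reason, no blinding is described, and results arrive at different times in the two arms. A reason edited after the result could turn even-handed noise into differential selection. This also stands, and it limits the filter to the reason recorded when the order was placed.

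Fourth, a reader might infer that starting the clock at the order date is an error because a result cannot shorten days before the specimen. The documents do not support that. Calendar-date counting makes a same-day order and specimen contribute no extra days. Wards that know their arm might sample sooner, an effect that a specimen-based start would hide. Total days also match the cost question. The start date is a trade-off.

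**Conclusion.** The point holds as a cheap improvement to the endpoint definition. The written rule admits other-reason isolation into an endpoint labelled as due to CDI, although the field that would exclude it is already being extracted. The consequence is dilution and extra variance. A reader might infer bias, but the rule as written applies alike in both arms and nothing in the documents points to a systematic difference.

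The size is unknown. A reader might take 41% and 24% as expected losses of information. They are not: the share of other-reason orders, their length, the SDs and the 1-day saving are all assumed, and the 10-day (SD 10) other-reason episodes drive the result. Depending on the assumed SD and clustering, the cost in power runs from negligible to material. The plan contains no power calculation that shows the loss to be affordable.

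**What to change.** In Methods, define the primary endpoint as days on contact precautions for orders whose SCM reason, as recorded when the order was placed, is CDI or diarrhea/gastroenteritis. Counting both categories makes a switch between them irrelevant. Tie the 7-day window to specimen collection and state its direction, so that it applies to every tested patient, including those who test negative. Add a rule for concurrent reasons, and say how a tested patient with no qualifying order enters the analysis.

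Keep any-reason isolation days as a sensitivity analysis and for the costing. Report days counted from the later of order and specimen collection as a supportive analysis, not as the primary definition.

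The cost is wording. Reason and start/stop dates are already to be extracted and linked to specimen results, and the antibiotic outcome already depends on when the specimen was collected. The extraction must preserve the reason as first recorded. The downside is that some reasons will be misrecorded and some patients will have more than one; the any-reason analysis checks both.

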where y_i is the outcome variable of interest (such as the hours that a patient spends in isolation or the days of hospitalization); $POCT_i$ is a dummy variable indicating whether the patient had a NPT test; Z_i is a vector of individual-specific variables, including age, gender, CDI status and severity, and the like; H_i is a set of dummies indicating ward; T_i is a set of dummies indicating season or month; and u_i is an individual-specific error term. This approach allows us to identify the effect of NPT testing independent of patient, ward and season. In addition, the NPTT dummy can be interacted with other variables to see whether the impact of NPT testing is higher for certain types of patients

Beyond evaluating the relative merits of NPT versus centralized testing, studies will also look at the microbiology of CDI in this study. Specifically, we will conduct several laboratory methods to examine antibiotic resistance and genetic variation in CDI. For example, whole genome sequencing of cultured CDI isolates may inform us about the transmission of specific strains in our setting. Indeed, certain strains and states of gut dysbiosis may result in increased morbidity and mortality (Shahinas et al., 2012). We will look at the microbiome of patients in this study to determine if dysbiosis contributes to adverse clinical outcomes. We will also correlate the strain types with the results of testing to determine if genetic variation affects test performance. Cultured toxin-producing CDI isolates will serve as a gold standard to evaluate test performance.

Originality of the proposal:

It is our view that in the clinical laboratory arena NPT for CDI (described earlier) as a technology has already matured to a stage that translation of this technology into the clinical domain is now needed. As described previously, several formats including lateral flow are currently available through major diagnostic companies. The Infectious Diseases Society of America (IDSA) has recently recommended that rapid diagnostic testing can enhance antimicrobial stewardship by promoting appropriate antibiotic use for respiratory infections (Barlam et al., 2016). However, the recommendation is listed as “weak” with “low-quality evidence”.

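### Days of hospitalization are counted from admission, so the comparison carries pre-specimen days that a faster result cannot shorten; this probably costs precision but does not by itself cause bias.

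*Combined protocol and SAP*

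**What the plan says.** The end of Study Objectives lists hospital stay among the secondary outcomes: "Secondary outcomes will compare turn-around times from specimen submission to result, days of hospitalization, the number of days of antibiotic therapy". Methods then defines it: "Days of hospitalization will be defined as the difference between the admission and discharge date". The specimen is linked to the discharge database only "to determine during which acute care encounter the specimen was collected and the admission/discharge dates of that encounter"; its date does not start the count.

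Eligibility under Study Objectives reads: "The inclusion criteria will be diarrhea in adult patients admitted to four acute care hospitals in the Calgary region being tested for CDI". It sets no limit on the time between admission and test. The same section states how the intervention works: "NPT testing can deliver results within several hours, while typically off-site testing takes one to two days".

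Data Analysis offers, as an example, a linear model whose outcome may be "the hours that a patient spends in isolation or the days of hospitalization". It has ward dummies and month or season dummies, and its patient covariates are described thus: "Z_i is a vector of individual-specific variables, including age, gender, CDI status and severity, and the like". Days from admission to specimen are not named.

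The other duration outcomes start closer to the episode. Antibiotic therapy counts if "initiated on the day of and up to 48 hours after specimen collection for CDI testing", and isolation time starts on the date that contact precautions are ordered.

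**The concern.** Patients enter the study by being tested, and near-patient testing acts only by bringing the result forward. Whatever it does to length of stay, it does after the specimen. For an inpatient who develops diarrhea late in a long admission, most of the recorded stay may lie before that point. Those days differ between patients for reasons unrelated to the intervention. Unless the analysis removes that variation, it adds to the residual error of the treatment estimate.

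What is at stake is the chance of seeing a real effect on a named secondary outcome. The delay that can be saved is at most about one to two days per test, so any effect on stay is likely to be small, and small effects need precision.

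**Working it through.** **No figure to reproduce.** The documents give no SD of stay, no pre-specimen days, no correlation, and no significance level, power or target difference for this outcome. The size can only be shown over assumed ranges.

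**Step 1: is the estimate biased?** Write total = pre + post. The example model is linear, so its treatment coefficient is a difference in mean days. If mean pre-specimen stay is equal in the two arms, the difference in mean total stay equals the difference in mean post-specimen stay. The target is unchanged.

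**Step 2: precision.** Let r = SD(pre)/SD(post) and rho = their correlation, both taken within ward after the other model terms. The ward dummies already absorb differences between wards.

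Var(total)/Var(post) = 1 + r² + 2·rho·r

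The standard error is multiplied by the square root of this ratio.

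| r | rho = 0: variance ratio | SE multiplier | rho = 0.4: variance ratio | rho = −0.3: variance ratio |
|---|---|---|---|---|
| 0.25 | 1.06 | 1.03 | 1.26 | 0.91 |
| 0.5 | 1.25 | 1.12 | 1.65 | 0.95 |
| 1.0 | 2.00 | 1.41 | 2.80 | 1.40 |

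The ratio exceeds 1 only if r² + 2·rho·r > 0, that is, rho > −r/2. At r = 0.25 the break-even is rho = −0.125. If nearly everyone is tested at admission, r is close to 0 and so is the loss.

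**Step 3: illustration in power.** Assume SD(post) = 10 days, a true effect of 1 day, two-sided alpha 0.05 and independent patients (clustering ignored). Take n = 1578 per arm, which is the six-month total under Study Objectives; 2 × 1578 = 3156, close to the planned enrolment of about 3000.

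- From specimen: SE = 10 × √(2/1578) = 0.356, and power is 80.2%.
- From admission, rho = 0: power is 77.8% at r = 0.25, 71.0% at r = 0.5 and 51.0% at r = 1.
- Patients per arm for 80% power: 1570 from specimen, against 1963 (r = 0.5) or 3140 (r = 1) from admission.

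**Step 4: simulation.** In 4000 simulated trials of the same size, 40% of patients had no pre-specimen days and the rest had exponential pre-specimen stay with mean 10 days. Post-specimen stay was skewed with SD 10, and the effect of −1 day fell on post-specimen stay only.

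| Analysis | Mean estimate | SE |
|---|---|---|
| Total stay | −0.99 | 0.480 |
| Post-specimen stay | −1.00 | 0.356 |
| Total stay adjusted for pre-specimen days | −1.00 | 0.356 |

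Here Var(pre) = 0.6 × 200 − 6² = 84, so r² = 84/100 = 0.84. The formula predicts an SE ratio of √1.84 = 1.36; the simulation gives 0.480/0.356 = 1.35. Both remedies recover the lost precision, and the mean estimate is essentially the same in all three.

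**The case against.** Five points can be made for the plan.

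1. *Total stay is a standard measure and the natural one for costing.* This stands. The economic evaluation needs it, and moving the clock for the effectiveness comparison does nothing for costing precision.
2. *The covariate list is open and the model is only an example.* True, so pre-specimen stay is not excluded. But an open-ended phrase does not prespecify a covariate, and nothing else in the documents restarts the count at the specimen.
3. *The size is unknown.* This stands. Ward dummies make the relevant r a within-ward ratio, the power figures ignore clustering, and a modest negative correlation can remove or reverse the loss. A positive correlation makes it larger.
4. *Specimen timing is not protected by randomization.* This is the strongest point. The specimen is taken after the ward is allocated, and the documents describe no blinding. If near-patient testing led staff to test half a day earlier with discharge unchanged, specimen-to-discharge stay would be half a day longer in that arm with no real effect. An adjusted analysis can shift in the same way, because it conditions on a variable arising after allocation. Total stay is immune.
5. *The primary endpoint is untouched.* This stands.

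A reader might also infer that counting from admission dilutes or biases the estimated difference. The documents do not support that: with pre-specimen days balanced, the difference in mean days is the same (Step 1).

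**Conclusion.** The point holds as a probable loss of precision on one secondary outcome. As written, the comparison includes days that a faster result cannot shorten, and no named covariate removes them. At rho = 0 the standard error would be about 3%, 12% or 41% larger at r = 0.25, 0.5 or 1.

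These figures rest on assumed values of r and rho and treat patients as independent within wards. They show what could happen and do not estimate this trial's loss. The direction is plausible because eligibility sets no limit on time to test. The loss disappears if rho is below −r/2 or if most patients are tested at admission.

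Two stronger conclusions are tempting. One is that a large loss has been shown; it has not, since the documents contain no data on stay. The other is that changing the definition is a pure gain; it is not, because the specimen date could itself respond to the allocation.

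**What to change.** Before analysis, amend Methods and Data Analysis in one of two ways for the effectiveness comparison:

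- define the outcome as discharge date minus collection date of the first specimen in the encounter; or
- keep total stay and prespecify days from admission to first specimen as a covariate in Z_i.

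With either choice:

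- keep unadjusted total stay as a sensitivity analysis and for costing; and
- report days from admission to first specimen by arm. A difference between arms, or disagreement between the main and total-stay estimates, would warn that testing behaviour changed with allocation.

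This is a cheap improvement. Specimen results are already to be linked to admission and discharge dates by health number, and the antibiotic definition already needs the collection date. No extra patients, data sources or procedures are required. The price is the exposure to specimen timing described above, which the two added reports are there to check.
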